SUSAR	Suspected Unexpected Serious Adverse Reaction
TDI	Transition Dyspnoea Index
TLCO	Transfer factor for Carbon Monoxide
TMF	Trial Master File
TMG	Trial Management Group

TSC	Trial Steering Committee
UAR	Unexpected Adverse Reaction
UE	Unexpected Event
UoB	University of Birmingham
UK	United Kingdom
VAS	Visual Analogue Score

DEFINITIONS

Term	Abbreviation	Description
Oxygen de-saturation on exercise	DSAT	Defined as dropping of oxygen levels as measured by a finger probe from normal to below 88%.
MRC Dyspnoea Score	MRC score	This is a validated measure of disease severity irrespective of patient's FEV1 in relation to breathlessness (dyspnoea). It is graded from 1 to 5 (5 being the most severe).
Gender-Age-Physiology score	GAP score	A score accounting concurrently for patient age, gender, FVC and D_{LCO} , where a higher score is associated with increased risk of mortality.

TRIAL SUMMARY

Title:

Ambulatory Oxygen Therapy for Pulmonary Fibrosis (OXYPuF)

Primary Objective:

To determine whether ambulatory oxygen therapy (AOT) is clinically and cost effective in patients with idiopathic pulmonary fibrosis (IPF).

Secondary Objectives:

- Determine whether breathlessness, determined by sub-scales of the King's Brief Interstitial Lung Disease (K-BILD) is superior after AOT compared to standardised breathlessness advice at 6 months.
- Determine whether MRC dyspnoea score, is superior after AOT compared to standardised breathlessness advice at 6 months.
- Determine whether exercise capacity and physical activity, as measured by the six minute walk test (6MWT) or a sit to stand test (depending on local policy), and a self-reported activity questionnaire (International

Physical Activity Questionnaire; IPAQ) respectively, is superior after AOT compared to standardised breathlessness advice at 6 months

Trial Design

A multicentre randomised controlled, open-label, pragmatic clinical trial, with internal pilot phase, designed to test both the clinical and cost effectiveness of AOT in patients with IPF.

Participant Population and Sample Size

260 consenting adults diagnosed with IPF confirmed via a multidisciplinary team (MDT) meeting or an IPF specialist.

Setting

Approximately 20 hospital outpatient clinics or community oxygen services.

Eligibility Criteria:

Inclusion

- Aged 18 or over
- Clinically diagnosed IPF, confirmed by an ILD MDT linked to an NHS specialist commissioned IPF service
- Breathlessness with MRC dyspnoea score ≥2
- Willing and able to comply with completion of questionnaires out to 6 months post-randomisation
- Able to complete a 6MWT or 1 minute sit to stand test
- Able to use oxygen safely in the opinion of the local investigator

Exclusion Criteria

- Unable to provide informed consent
- Requires LTOT, defined by need for resting oxygen in the opinion of the local investigator
- Life expectancy <6 months
- On the active transplant list
- Previous acidotic hypercapnic respiratory failure (AHRF) requiring non-invasive ventilation (NIV)

Intervention Arm

Ambulatory Oxygen Therapy and standardised breathlessness advice.

Control Arm

Standardised breathlessness advice.

Outcome Measures:

Primary Outcome

Total K-BILD score at 6 months.

Secondary Outcomes at six months after randomisation unless otherwise stated

- Subscales within K-BILD (breathlessness, activity, chest symptoms)
- Exercise capacity using the 6MWT or 1 minute sit to stand

- MRC dyspnoea score
- Physical activity using the IPAQ
- Sleepiness using the Epworth Sleepiness Scale
- Hospitalisations (all cause and IPF specific)
- Cough using a 6 point Visual Analogue Scale (VAS)
- Targeted adverse events
- Mortality (6 months, and from medical record only at 12 months)
- Medication use: benzodiazepines, antifibrotics; ACEis and opiates for breathlessness
- Completion of pulmonary rehabilitation
- Acceptability of AOT
- Cost-effectiveness (using EQ-5D-5L, and scheduled and unscheduled health service use relating to IPF).

TRIAL SCHEMA

[figure not shown]

TABLE OF CONTENTS

1. BACKGROUND AND RATIONALE	17
1.1 Background	17
1.2 Trial rationale.....	18
1.2.1. Justification for participant population	18
1.2.2. Justification for design	19
1.2.3. Justification for choice of intervention(s)	19
1.2.4. Justification of choice of primary outcome(s)	19
2. AIMS AND OBJECTIVES.....	19
2.1. Internal pilot objectives.....	19
2.2. Main trial objectives.....	20
2.2.2. Economic aims and objectives	20
2.2.3. Mechanistic aims and objectives	20
3. TRIAL DESIGN AND SETTING.....	20
3.1. Trial design.....	20
3.2. Trial setting.....	20
3.3. Sub-studies	21
3.3.1 Qualitative sub-study	21
3.3.2 Objective physical activity study	21
3.4. Assessment of risk	22
4. ELIGIBILITY	22
4.1. Inclusion criteria	22
4.2. Exclusion criteria	22
4.3. Co-enrolment.....	22
5. CONSENT	22
6. SCREENING, RANDOMISATION and BLINDING	23
6.1. Identification	23
6.2. Screening	24
6.3. Randomisation	24

1. BACKGROUND AND RATIONALE

1.1 Background

Idiopathic Pulmonary Fibrosis (IPF) is the most common of a disparate group of conditions that lead to pulmonary fibrosis. Studies suggest that the incidence (4.6/ 100 000) and prevalence is rising over time, even allowing for more accurate and earlier identification (1, 2). Prognosis is poor with inexorable decline towards respiratory failure. Duration from initial symptoms to presentation at specialist interstitial lung disease (ILD) clinics can be variable, adding to the difficulty in predicting prognosis in individual cases and to the frustration of sufferers, their families and their supporting clinical teams. Whilst overall, there is a linear decline in forced vital capacity (FVC), for some this is experienced as a steady deterioration, for others, there are periods of stability with episodes of accelerated decline, which does not always have a tangible, treatable trigger. There may be increasing dyspnoea and plummeting functional status over a short period; median survival is approximately 3 years from the time of diagnosis (3).

The GAP score, which uses FVC and transfer capacity of the lung for carbon monoxide (TLCO) in addition to age and gender, has been used in research settings to predict mortality, however, for an individual in the clinic this is a less useful predictor (4). Individual tolerance of falling FVC, gas transfer and exercise desaturation in terms of dyspnoea can also make an individual's experience and level of disability difficult to predict. A significant proportion of time from diagnosis is spent with debilitating symptoms and increasing dependency. Healthcare costs are considerable (5), comprising supportive measures for breathlessness, pulmonary rehabilitation and antifibrotic agents such as nintedanib and pirfenidone in selected patients (6). Treatment with antifibrotics in the UK is centrally commissioned and is of high cost. In order to be eligible, the FVC must be between 50 and 80%, a figure based on trial data. However some groups, such as those with emphysema or premorbid supranormal physiology, for example, will not be eligible for treatment until later in their disease journey. These antifibrotic treatments slow progression of FVC decline (7), reduce the risk of acute respiratory deteriorations (8), which are associated with high morbidity and mortality, and reduce the risk of mortality (8). There is however, only limited evidence to suggest that there may be an improvement in cough (9), and nothing to support that these drugs confer a reduction in dyspnoea. Consequently, concomitant treatment approaches are still required for these symptoms; oxygen could address the latter. Furthermore, antifibrotics are associated with clinically significant side effects, primarily gastrointestinal in nature, limiting their tolerability. The loss of appetite can increase weight loss, sarcopenia and morbidity.

Considerable uncertainty exists on the use of supportive treatments used in other respiratory diseases, such as oxygen. Supplemental oxygen is commonly prescribed in routine clinical practice, with the aim of improving dyspnoea, exercise capacity and health-related quality of life (HRQoL); its use may be considered to be the standard of care (10). Current recommendations for long-term oxygen therapy (LTOT) for resting hypoxaemia in IPF are largely extrapolated from trials conducted in Chronic Obstructive Pulmonary Disorder (COPD), where a survival benefit is well established (11), but there are factors in IPF which may impact efficacy. In particular, exercise desaturation is often a prominent problem in early disease, hastening deconditioning and limiting ability to engage with exercise, suggesting that use in this setting (rather than purely as LTOT) would need to differ. The most recent recommendations are from a Delphi consensus of 45 experts from 17 countries (12); use of supplemental oxygen for patients with fibrotic ILD is recommended where there is severe resting hypoxemia or exertional hypoxemia with attributable symptoms or exercise limitation.

Surprisingly, given the above consensus, there is very little conclusive evidence in IPF on whether oxygen is beneficial. LTOT use in marked hypoxia is not controversial, given that the mechanism of benefit (to prevent pulmonary hypertension/*cor pulmonale*) is likely the same as COPD, although a recent systematic review was unable to draw conclusions due to high levels of bias in relevant studies (n=2670 patients) (13). However, opinions of ambulatory oxygen therapy (AOT) are far less certain; one systematic review concluded no benefit (13) and noted that the studies included in the review were largely observational designs prone to bias. Some studies found a small benefit on objective exercise capacity (14-16) and a small, open-label, crossover, randomised controlled trial (RCT; n=84) is suggestive of AOT use improving HRQoL short term (17). The impact on long term HRQoL remains unknown, suggesting that a larger scale, longer term study in IPF is required. Furthermore, access to oxygen is dependent on local funding and criteria as well as practice of individual clinicians (18), resulting in great variability in access. Given that this intervention is expensive and burdensome (19), establishing benefit or lack thereof, could help target those

who would most benefit from AOT with the aim of reducing inequity in oxygen availability. If oxygen is not beneficial, focus should be on supportive measures i.e. counselling, pulmonary rehabilitation and early referral to palliative care (20).

1.2. Trial rationale

In other conditions in which oxygen has evidence of patient benefit when used long term (typically ≥ 12 or ≥ 15 hours/day), such as COPD (11, 21), a systematic review has shown no consistent benefit of AOT (22). The prescription of AOT in COPD has historically been governed by an improvement in exercise capacity or Borg dyspnoea scores, wherein a 10% improvement in distance walked or reduction of ≥ 1 point in the Borg Score indicates it should be used in patients with desaturation of $>4\%$ on exertion (23). The systematic review showed there is not a benefit of this magnitude. Furthermore, compliance with AOT may be low, and COPD patients have reported multiple reasons why they did not use it as prescribed, namely they received no instruction on how to use it; were uncertain of the benefits; were afraid it would run out while they were using it; were embarrassed at being seen with it in public; and were unable to carry it because of cylinder weight (19). These factors are likely to be common to IPF patients, hence it is important to test AOT in a pragmatic RCT, to obtain information on effects in a real-life setting, and to assess in adherence and acceptability. Given that these attitudes may impact recruitment, we plan to conduct all acceptability work during the pilot phase of the proposed trial.

1.2.1. Justification for participant population

Selection of patients for treatment may be important, and again there may be transferable lessons from use of AOT in COPD. In a review, two studies (24, 25) used exertional dyspnoea as their main inclusion criterion. Few studies specified “acute responders” as an inclusion criterion (i.e. those with $>10\%$ improvement in walking distance); interestingly however, seven studies (24-30) included a single assessment acute oxygen test for all participants as part of their protocol. All but one (29) demonstrated a significant mean improvement in exercise capacity for participants with acute oxygen therapy compared to compressed air. It would therefore seem that acute improvement in walking distance observed in a single assessment study is lost over time, given that overall the studies showed no benefits. This has implications for clinical practice as prescriptions for AOT might not be appropriate to assess based on an on-oxygen exercise capacity e.g. 6 minute walk test (6MWT) result. Some studies of AOT in COPD (27, 29-32) were carried out as part of pulmonary rehabilitation. Although no benefit of long term AOT was demonstrated, exercise capacity (particularly 6MWT) in the pulmonary rehabilitation studies exceeded that of the domiciliary studies (24, 25), regardless of whether patients were randomised to AOT or placebo. Furthermore, the improvement in 6MWT distance gained by pulmonary rehabilitation far exceeded that gained by AOT (30), thus supporting guidance (23) that any assessment of AOT should be made following pulmonary rehabilitation. Whilst rehabilitation is beneficial in ILD (33), the effects tend to be sustained for a shorter period (34), and it is recognised that any improvement in exercise capacity can be negated by the weight of the AOT if carried by patients alone (35, 36). Tolerating this weight may be more likely in patients whose fitness is optimised by recent rehabilitation – consequently date of rehabilitation could be a confounder in studies of AOT and our protocol therefore accounts for this.

Participants in OXYPuF will have a clinical diagnosis of IPF and may have any disease severity, with or without anti-fibrotic treatment. Whilst MRC dyspnoea score ≥ 2 is more likely to occur in people who have more severe disease, the mechanism by which oxygen acts is likely to be independent of this, and of anti-fibrotics; this plus a desire for this trial population to reflect those likely to receive the intervention in real life has prompted us to keep the inclusion criteria broad. We will, however, balance the two intervention groups for key features such as disease severity and anti-fibrotic use.

We recognise that keeping the inclusion criteria as broad as possible, in order to ensure results are likely to be applicable to the whole IPF population in the United Kingdom, is desirable and for this reason have not included any other severity features (e.g. % predicted FVC) or prior treatment expectations, though we will balance this between intervention groups. In addition, patients with co-existent co-morbidities which might impact hypoxia and exercise tolerance (e.g. heart failure) will be eligible to participate, although this will be recorded and explored within the data to examine if sub-group effects are present. Such individuals would commonly be excluded from drug trials, but

constitute a large proportion of the IPF population in real life; for example, heart failure occurs in 21-30% of IPF patients (4, 40). Including such patients keeps our results generalisable.

We will therefore recruit 260 patients with IPF and an MRC dyspnoea score ≥ 2 from centres in the UK.

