6.4. Randomisation process

Randomisation will be provided by a secure online randomisation system at the Birmingham Clinical Trials Unit (BCTU) (available at <<insert web address>>), thereby ensuring allocation concealment. Unique log-in usernames and passwords will be provided to those who wish to use the online system and who have been delegated the role of randomising participants into the study as detailed on the **OXYPuF Trial Signature and Delegation Log**. These unique log-in details must not be shared with other staff and in no circumstances should staff at sites access either the randomisation process or clinical investigation database using another person's login details. The online randomisation system will be available 24 hours a day, 7 days a week, apart from short periods of scheduled maintenance. In the event of the online system not being available a telephone toll-free randomisation service ([name]) is available Monday to Friday, 09:00 to 17:00 UK time, except for bank holidays and University of Birmingham closed days. The availability of telephone randomisation may be reduced due to unforeseen circumstances such as epidemic/pandemic and/or natural disasters.

Following randomisation, a confirmatory e-mail will be sent to the randomiser, local PI, local Research Nurse, and trial manager.

The local research team should add the participant to the **OXYPuF Participant Recruitment and Identification Log** which links participants with their Registration/Trial Number. PIs must maintain this document securely and it must

not be submitted to the Trial Office. The *OXYPuF* Participant Recruitment and Identification Log should be held in strict confidence. [Randomisation method](#)

Participants will be randomised at the level of the individual in a 1:1 ratio to either AOT and standardised breathlessness advice or standardised breathlessness advice alone.

A minimisation algorithm will be used within the online randomisation system to ensure balance in the treatment allocations over the following variables:

- Centre
- Desaturation to <88% on 6MWT or equivalent exercise test
- Current or recent (within 6 months) pulmonary rehabilitation
- Current antifibrotic use

randomised To avoid the possibility of the intervention allocation becoming predictable, a random element will be included in the algorithm. Full details of the randomisation specification will be stored in a confidential document at BCTU.

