15.2.3 Planned subgroup analyses

Subgroup analyses will be limited to the same variables used in the minimisation algorithm (see section 6.4.1.), desaturation at baseline, 6MWT or 1 minute sit to stand and performed on the primary outcome only. The effects of these subgroups will be examined by including an intervention group by subgroup interaction parameter in the regression model, which will be presented alongside the effect estimate and 95% confidence interval within subgroups. The results of subgroup analyses will be treated with caution and will be used for the purposes of hypothesis generation only.

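### Section 1.2.1 promises balance on % predicted FVC and a look at heart-failure subgroups, but the allocation, model and subgroup sections of the protocol deliver neither directly

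*Protocol*

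**What the plan says.** Section 1.2.1 opens entry to IPF of any severity and offers balance between arms as the safeguard. It states this generally, "We will, however, balance the two intervention groups for key features such as disease severity and anti-fibrotic use", and then with a named variable: the criteria "have not included any other severity features (e.g. % predicted FVC) or prior treatment expectations, though we will balance this between intervention groups". On co-morbidities that may affect hypoxia and exercise tolerance, with heart failure as the example, it says "this will be recorded and explored within the data to examine if sub-group effects are present", and notes that "heart failure occurs in 21-30% of IPF patients".

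Section 6.4 then fixes the allocation method: "A minimisation algorithm will be used within the online randomisation system to ensure balance in the treatment allocations over the following variables". Four variables follow: centre, "Desaturation to <88% on 6MWT or equivalent exercise test", pulmonary rehabilitation (ongoing or in the past six months), and antifibrotic use. Section 15.2 adjusts for these four plus baseline K-BILD, with centre as a random effect and the others fixed.

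Section 15.2.3 states: "Subgroup analyses will be limited to the same variables used in the minimisation algorithm". It then also names baseline desaturation and the exercise test. Subgroup work is confined to the primary outcome, is done through interaction terms with estimates inside each subgroup, and is labelled hypothesis-generating.

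FVC and DLCO are baseline items in Table 2, and section 9 accepts spirometry from the previous six months. The definitions table describes a GAP score built on age, gender, FVC and DLCO, but the allocation and analysis sections make no use of it.

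**The concern.** Three statements do not fit together.

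- **FVC.** The one severity measure that 1.2.1 names as balanced appears in neither the minimisation list nor the covariate set. A reader who relies on 1.2.1 would think it was controlled by design.
- **Heart failure.** The exploration promised in 1.2.1 is excluded by the restrictive wording of 15.2.3.
- **Centre.** Because the subgroup list is defined by reference to the minimisation list and no exception is made, centre becomes a subgroup variable. With about 20 sites it cannot give useful within-subgroup estimates.

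At stake are some precision and some protection against a chance difference in lung-function severity, together with a subgroup list that omits a factor the protocol says it will examine and contains one it cannot examine usefully. The trial's error rates and sample size are not affected.

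**Working it through.** **The plan's own figure.** Section 15.1 gives a difference of 4.0, SD 8.85, 90% power and two-sided 5%. The normal approximation is n = 2 × (1.960 + 1.282)² × 8.85² / 4² = 102.9, so 103 per arm. With the noncentral t distribution, power is 89.8% at 103 and 90.04% at 104, so the stated 104 is reproduced. Then 208 / 0.80 = 260, also as stated. Nothing below disputes this.

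**Where each factor appears**

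| Factor | Promised in 1.2.1 | Minimised (6.4) | Adjusted (15.2) | Subgroup (15.2.3) |
|---|---|---|---|---|
| % predicted FVC | balance | no | no | no |
| Antifibrotic use | balance | yes | yes | yes |
| Exercise desaturation | not named (a severity marker) | yes | yes | yes |
| Heart failure | subgroup exploration | no | no | no |
| Centre | no | yes | yes (random) | yes, by cross-reference |

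**Chance imbalance in FVC.** With 104 evaluable per arm, and allocation treated as simple randomisation with respect to FVC, the standardised baseline difference has SD √(2/104) = 0.139, so its 95% limits are ±1.96 × 0.139 = ±0.27 SD. With all 130 per arm the limits are ±0.24 SD. Correlation of FVC with the minimised variables would narrow both.

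**Effect on the K-BILD estimate.** Let r be the correlation of FVC with K-BILD (taken as equal at baseline and 6 months) and ρ the correlation between baseline and 6-month K-BILD. The documents give neither, so r = 0.3–0.5 and ρ = 0.5–0.7 are assumptions.

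- With no adjustment, the shift is 1.96 × 0.139 × 8.85 × r = 2.41 × r, that is 0.72 (r = 0.3) to 1.20 (r = 0.5) points.
- With the planned baseline K-BILD adjustment, the shift is 2.41 × r(1 − ρ)/√(1 − r²):

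| | ρ = 0.7 | ρ = 0.5 |
|---|---|---|
| r = 0.3 | 0.23 | 0.38 |
| r = 0.5 | 0.42 | 0.69 |

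The planned analysis therefore leaves about 0.2 to 0.7 points, or 6–17% of the 4-point target, before any further reduction from adjusting for desaturation and antifibrotic use.

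**Centre as a subgroup.** 208 / 20 = 10.4 evaluable per site, or 5.2 per arm. The SE of a within-centre difference is 8.85 × √(2/5.2) = 5.49, and the 95% half-width is 1.96 × 5.49 = 10.8 points.

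**Heart failure as a subgroup.** At 21–30% of 208, 43.7 to 62.4 evaluable participants would have heart failure. With a and b the numbers with and without it, split equally between arms, the SE of the interaction is 8.85 × √(4/a + 4/b).

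- 21%: SE = 3.01; power for a 4-point interaction = Φ(4/3.01 − 1.96) = 26%.
- 30%: SE = 2.68; power = Φ(4/2.68 − 1.96) = 32%.

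**The case against.** A reader might infer that the design has no protection against severity imbalance. The documents do not support that. Exercise desaturation is minimised and adjusted for, and it is a severity marker close to the mechanism of the intervention. Antifibrotic use is minimised too, and section 1.1 ties eligibility for those drugs to an FVC range, so it is partly a proxy for FVC. Baseline K-BILD is in the model. The general promise is therefore partly kept, and only the FVC example fails.

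A reader might also take the unadjusted shift of 0.7 to 1.2 points (18–30% of the target) as the error in the trial. It is not. That analysis is not planned, and chance imbalance under randomisation is not bias: it is a component of the unadjusted 95% half-width of 2.41 points, already counted in the standard error. The correlations are unsupported by the documents, and section 1.1 itself says that tolerance of falling FVC varies and that GAP predicts less well for an individual.

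On subgroups, 15.2.3 goes a little beyond the minimisation variables, since it also names the exercise test. The promised exploration could be an informal look, and an analysis plan not at hand may list one. But no reading of 15.2.3 admits heart failure, and its restriction is the protocol's own. Centre enters only through a cross-reference and is a random effect in 15.2, so it cannot be said that a fixed interaction with 19 degrees of freedom is planned. As written, though, centre is not excluded, and estimates within each subgroup are promised. The hypothesis-generating label limits the harm.

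**Conclusion.** The mismatches are in the text and should be reconciled. Their consequence is modest. The primary comparison is valid under randomisation, and the sample size stands. What is missing is direct control of the severity measure that 1.2.1 names. Under the assumed correlations (0.3–0.5 for FVC with K-BILD, 0.5–0.7 between the two K-BILD scores), adjusting for it would remove a possible chance shift of about 0.2 to 0.7 points at the 95% limits and add a little precision.

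The centre subgroup is uninformative at about ±11 points per site, assuming 20 equal sites, 208 evaluable and SD 8.85. The heart-failure subgroup would have only about 26–32% power for a 4-point interaction, so listing it honours the stated intention but will not settle the question.

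It may be tempting to conclude that FVC should be added to the minimisation algorithm. The documents do not make that necessary: model adjustment handles chance imbalance, whereas a new allocation factor would need cut-points and a change to the randomisation system, using spirometry that may be up to six months old.

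**What to change.** - **Section 15.2:** add baseline % predicted FVC as a fixed, continuous covariate in the primary model. GAP is an alternative. State how a missing baseline value will be handled.
- **Section 1.2.1:** reword to say that exercise desaturation and antifibrotic use are balanced by allocation, and that FVC is adjusted for in the analysis.
- **Section 6.4:** leave the minimisation algorithm unchanged.
- **Section 15.2.3:** write the subgroup variables out instead of cross-referring, exclude centre, and add heart failure as a hypothesis-generating subgroup with a note on its low power.

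The cost is an amendment to wording, one more model parameter, and a rule for missing baseline spirometry. No new data are needed for FVC, and 1.2.1 already says that co-morbidity will be recorded. If the team prefers not to adjust for FVC, the minimum is to withdraw the FVC balance statement from 1.2.1. That removes the contradiction but gives up the small gain. The changes should be fixed before outcome data are seen by arm.
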